3.2. Study Design Rationale

Blinding, Control, Study Phase/Periods, Treatment Groups and Treatment Duration

Subjects enrolled in this study will participate in 2 sequential treatment phases/periods:

- **DB treatment phase:** a 52-Week (12-Month) placebo-controlled double-blind treatment phase. Eligible subjects enrolled will receive either JNJ-54861911 (10-mg or 25-mg q.d.) or placebo (q.d.). Subjects will continue on their current treatment regimen assigned under the 54861911ALZ2002 study (placebo, 10-mg or 25-mg q.d. JNJ-54861911). Subjects who received an active dose different from 10-mg or 25-mg JNJ-54861911 in 54861911ALZ2002 study will be receiving the closest dose available in the DB treatment phase (i.e. subjects receiving 50 mg in study 54861911ALZ2002 will be assigned to 25 mg JNJ-54861911).
- **OL treatment phase:** an open-label treatment phase during which subjects who received placebo in DB treatment phase will be randomized with equal chance to one of two JNJ-54861911 dose levels (5-mg q.d. or 25-mg q.d. JNJ-54861911). Subjects who were receiving 10 mg q.d. JNJ-54861911 will have their dose reduced to 5 mg q.d., while subjects who were receiving 25 mg q.d. will continue to receive that dosage.

A treatment duration of 52 weeks in the DB treatment phase combined with the duration of treatment under the parent protocols is deemed sufficient to assess any emergent safety aspects (treatment induced effects) of JNJ-54861911 in relation to placebo treatment as outlined below

(‘Safety Evaluations’). A placebo control of 52 weeks in this study is considered to be acceptable as efficacy of JNJ-54861911 has not yet been demonstrated, no treatment is available yet and subjects can continue on normal standard care (symptomatic treatment) as outlined in Section 8. Prestudy and Concomitant Therapy.

A placebo control will be used in the DB treatment phase (Day 1 to Week 52 [Month 12]; placebo-controlled) to explore the frequency and magnitude of changes in clinical endpoints that may occur in the absence of active treatment during the first year of treatment in this study. It is yet unclear in which time frame potential adverse event patterns may arise. It may be difficult to separate them from actual aging or AD-related patterns (e.g., cognitive decline, MRI microhemorrhages, amyloid related imaging abnormalities-edema or effusion [ARIA-E]). To control for these factors a placebo group is warranted over a limited time.

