Specific dermatologic and ophthalmologic examinations, as described in Section 9.2, Safety Evaluations have been implemented in this study as potential BACE1- or BACE2-linked toxicities (e.g. melanin deposition changes and retinal abnormalities) have been described in the literature (e.g. BACE1 or BACE2 knock-out mice). With the exception of fur discoloration resulting in progressive lightening of the fur from normal dark brown to paler cream or grey, which was seen in one species only (Tg mice in the 6 month carcinogenicity study), however, these toxicities have not been observed in nonclinical chronic studies with JNJ-54861911. Note that cases of lightening of skin, lightening of hair or ophthalmological adverse events are considered adverse events of special interest (AESI) and are subject to reporting timelines as described in Section 12.3.4.

As a result of the newly identified case of drug-induced hepatotoxicity, if at any time during treatment a subject has an ALT or AST result that is $\geq 3 \times$ ULN, the test should be repeated within 24 - 72 hours and, if confirmed, the further evaluation and management procedures described in [Attachment 1](#) should be followed.

In addition to the (safety) MRI assessments performed under the 54861911ALZ2002 study (if applicable), safety MRIs will be collected in this study during both DB and OL treatment periods, as indicated in the Time and Events Schedule, to monitor any treatment-emergent abnormalities including ARIA-edema or effusion (E) and ARIA-hemosiderin (H). Additional annual MRIs will be collected in OL period. If any safety related changes are observed (e.g. ARIA-E), additional safety MRIs may be collected at a frequency recommended by the DRC.

In case of any changes observed in any of the safety measures performed that are considered not clinically significant or do not have a direct clinical symptomatology as assessed by the investigator, they should be closely monitored, with a potential increased safety monitoring frequency as deemed appropriate by the investigator. In addition, these findings will be presented to the DRC, who will make recommendations regarding the safety and continuation of the study as per its charter.

Biomarker Collection

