9.2.8. Magnetic Resonance Imaging

All subjects will receive an MRI in this study at the time points indicated in the Time and Events scheduled for primarily safety reasons.

An additional baseline MRI may be collected (during screening or Day 1) in case subjects are enrolled from future JNJ-54861911 studies who did not obtain an adequate MRI under the parent protocol 6 months prior to first dosing in this study. For subjects who participated in study 54861911ALZ2002 no baseline MRI scan is to be collected as an MRI was collected at Month 6 under the parent protocol.

Collection of MRI data is primarily for safety reasons. MRI scans will be collected during DB treatment phase (up to and including Week 52 [Month 12]) and OL treatment phase (annual). Additional MRI scans may be collected based on emerging safety data (e.g., ARIA-E or H) with a frequency as recommended by the DRC.

Imaging sequences for all pre-specified protocol MRI studies will consist of an identical set of pulse sequences, including FLAIR and T2* sequences, as described in the MRI imaging manual.

Global and regional brain volumes and regional cortical thickness will be derived from the volumetric MRI sequence and will include both cross sectional absolute measurements and longitudinal volume change. The regional volumes and regional cortical thicknesses that will be chosen for this study will include those anatomical areas that are most affected in AD.

All MRI data collected (screening and on treatment) will be sent to a core imaging lab for quality control purposes and for data management, image processing, data analysis, and archiving.

MRI image evaluation will be performed by a core imaging lab.

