11.5. Safety Analyses

All subjects receiving at least one dose of study drug will be included in the safety analysis. Descriptive statistics will be computed.

Adverse Events

The verbatim terms used in the CRF by investigators to identify adverse events will be coded using the Medical Dictionary for Regulatory Activities (MedDRA). All reported adverse events with onset during the treatment phase (i.e., treatment-emergent adverse events, and adverse events that have worsened since baseline) will be included in the analysis. For each adverse event, the percentage of subjects who experience at least one occurrence of the given event will be summarized by treatment group. Adverse events will also be tabulated by severity and by relationship to study drug and will be presented by treatment group. Serious adverse events will be summarized separately.

Summaries will be provided for all subjects receiving at least one dose of study drug in this study, and will include adverse events from this study as well as any preceding studies (e.g., study JNJ-54861911ALZ1005, JNJ-54861911ALZ2002 or any future Phase 1b or Phase 2 JNJ-54861911 clinical studies) as applicable for subjects who previously participated in that study, where appropriate.

Summaries, listings, datasets, or subject narratives may be provided, as appropriate, for those subjects who die, who withdraw due to an adverse event, or who experience a severe or a serious adverse event. Subjects with AESIs may be counted or listed.

Clinical Laboratory Tests

Laboratory data will be summarized by type of laboratory test. Descriptive statistics will be calculated for each laboratory analyte at baseline and at each scheduled time point, and for changes from baseline.

The number and percentage of subjects experiencing a laboratory result below or above normal reference ranges will be provided for each laboratory analyte by treatment group.

A listing of subjects with any laboratory result outside the reference ranges will be provided.

Electrocardiogram (ECG)

Heart rate and ECG intervals (RR, PR, QRS, and QT) as well as corrected QT intervals according to Bazett's formula (QTcB) and Fridericia's formula (QTcF) from the 12-lead ECG will be summarized at baseline and at each scheduled time point and for changes from baseline using descriptive statistics.

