The number and percentage of subjects with at least 1 occurrence of a treatment-emergent potentially clinically important QTc measurement (QTc value >450, >480, or >500 ms) or with a change from baseline in QTc >30 ms will be summarized by treatment group.

Data listings of subjects with any potentially clinically important values (QTc value >450, >480, or >500 ms) or with a change from baseline in QTc >30 ms will be provided.

Vital Signs

Descriptive statistics of pulse, blood pressure (systolic and diastolic) (supine and standing), temperature and body weight values and changes from baseline will be summarized at each scheduled time point.

Physical and Neurological Examination

The number and percentage of subjects with a change from normal at baseline to abnormal at any postbaseline exam will be tabulated by treatment group.

Subjects with abnormal findings will be presented in a data listing.

Dermatologic and Ophthalmologic Examination

Results of the dermatologic and ophthalmologic examinations (incl. OCT) will be presented by treatment group. Subjects with abnormal findings will be presented in a data listing.

Columbia Suicide Severity Rating Scale (C-SSRS)

Results from the C-SSRS will be tabulated by treatment group for all subjects receiving at least one dose of study drug in this study.

Safety MRI

The number and percentages of subjects with presence of ARIA-E, ARIA-H, and other MRI abnormalities found in the safety MRI assessments will be tabulated by treatment group.

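### The safety MRI table counts ARIA that is present, not ARIA that is new or increased, which dilutes the placebo comparison and cannot separate old from new findings in the open-label phase

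*Protocol*

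**What the plan says.** The Safety MRI paragraph of Protocol Section 11.5 is one sentence. It tabulates by treatment group "The number and percentages of subjects with presence of ARIA-E, ARIA-H, and other MRI abnormalities found in the safety MRI assessments". It names no reference scan and does not require a finding to be new or worse.

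Section 3.2 gives the purpose of the scans as "to monitor any treatment-emergent abnormalities including ARIA-edema or effusion (E) and ARIA-hemosiderin (H". On possible adverse event patterns, the same section warns: "It may be difficult to separate them from actual aging or AD-related patterns (e.g., cognitive decline, MRI microhemorrhages". Its stated remedy is the double-blind control arm: "To control for these factors a placebo group is warranted over a limited time".

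Some other lines of Section 11.5 do refer to baseline. Adverse events are limited to "treatment-emergent adverse events, and adverse events that have worsened since baseline". Physical and neurological findings are counted in subjects "with a change from normal at baseline to abnormal at any postbaseline exam". The QTc line counts treatment-emergent values or a change from baseline.

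On reference scans, Section 9.2.8 says that for subjects from ALZ2002 "no baseline MRI scan is to be collected as an MRI was collected at Month 6 under the parent protocol". That scan was taken after six months of parent-study treatment. In this study MRI is scheduled at Weeks 24 and 52 of the double-blind phase and every 48 weeks in the open-label phase.

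**The concern.** The counting rule does not match the purpose. The scans are there to find what emerges on treatment, but the table counts whatever is visible. A hemosiderin deposit that predates the first dose and is still visible at Week 24 or Week 52 makes its carrier a case, whichever arm the subject is in.

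Safety is the primary objective, and the 52-week double-blind phase is the only placebo-controlled look at ARIA in this study. A count that mixes old and new lesions weakens that comparison. After Week 52 placebo subjects move to 5 mg or 25 mg, and no control arm remains to absorb the background. If lesions persist, those acquired earlier then appear under whichever active dose the subject is taking.

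**Working it through.** **Inputs.** The protocol gives no ARIA rate, no baseline prevalence, no sample size and no power for this table, so it has no figure of its own to reproduce. All rates and sample sizes below are assumptions for illustration.

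- b: proportion with ARIA-H before treatment, equal in the arms and still visible on later scans; range 0% to 30%.
- p1, p0: risk of new ARIA-H on active and on placebo among subjects free of it at the start.

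**Formulas.**

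- Presence in an arm: q = b + (1 - b)p.
- Difference in presence: q1 - q0 = (1 - b)(p1 - p0).
- Standardized difference for presence: z = (q1 - q0) / sqrt[q1(1 - q1)/n1 + q0(1 - q0)/n0].
- For new lesions: the same form with p1 and p0, and with n1 and n0 multiplied by (1 - b), because only lesion-free subjects are at risk.

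**Illustration 1: p1 = 6%, p0 = 2%, 100 active and 50 placebo subjects.** At b = 20%, for example, q1 = 0.20 + 0.80 × 0.06 = 24.8% and q0 = 0.20 + 0.80 × 0.02 = 21.6%.

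| b | Presence, active | Presence, placebo | Difference (points) | Ratio | z, presence | z, new lesions |
|---|---|---|---|---|---|---|
| 0% | 6.0% | 2.0% | 4.0 | 3.00 | 1.29 | 1.29 |
| 10% | 15.4% | 11.8% | 3.6 | 1.31 | 0.62 | 1.23 |
| 20% | 24.8% | 21.6% | 3.2 | 1.15 | 0.44 | 1.16 |
| 30% | 34.2% | 31.4% | 2.8 | 1.09 | 0.35 | 1.08 |

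The absolute difference keeps 90%, 80% and 70% of its size at b = 10%, 20% and 30%. The ratio falls much faster. The standardized difference drops mostly because the variance rises.

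**Illustration 2: p1 = 10%, p0 = 3%, 30 subjects per arm.** The standard deviations are from 200,000 simulated trials.

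| b | Presence: difference / SD | New lesions: difference / SD |
|---|---|---|
| 0% | 0.070 / 0.063 = 1.11 | 0.070 / 0.063 = 1.11 |
| 20% | 0.056 / 0.112 = 0.50 | 0.070 / 0.071 = 0.99 |
| 30% | 0.049 / 0.123 = 0.40 | 0.070 / 0.076 = 0.92 |

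The pattern is the same: presence loses more than half of its signal relative to noise, and a count of new lesions loses little.

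**Open-label phase.** Take b = 20% from Illustration 1. At Week 52, 21.6% of placebo subjects carry ARIA-H. If those lesions persist, at least 21.6% of the same subjects appear as cases under 5 mg or 25 mg, even if the drug causes no new lesion. No concurrent control is left to subtract this.

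**Reference scan.** If the parent Month 6 scan served as baseline, any ARIA that arose in the first six months of treatment would be classed as pre-existing. A table of new findings is therefore only as good as the scan it refers to, and the protocol has to name that scan.

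**The case against.** Several points on the other side have weight.

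*The detail may belong in the analysis plan.* Section 11 calls its methods a general description, Sections 3.3 and 11.6 refer to a prespecified analysis plan that is not at hand, and shift tables are often left to such a plan. But the protocol is not silent here. It names the outcome to be counted, and a plan that follows it literally produces a prevalence table.

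*The placebo group already controls for background.* In the double-blind phase it does so in part: under equal b the direction is kept and the absolute difference shrinks only by (1 - b). A reader might infer that the table would be swamped by old microhemorrhages, or would conceal any excess on drug. The documents support neither. They give no baseline prevalence, the parent study's entry criteria are not described here, and at b = 0 the two counts are identical. Equal b is itself not assured, because Section 11 describes the subjects as self-selected.

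*The MRI line is not unique.* A reader might take it as the one line of Section 11.5 without a baseline condition. It is not: the counts of out-of-range laboratory results, the dermatologic and ophthalmologic results and the C-SSRS tabulation also have none. The mismatch that matters is with the purpose stated in Section 3.2.

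*ARIA-E.* The mechanism needs findings that predate treatment and persist. Nothing in the protocol shows that this applies to ARIA-E, so the argument concerns mainly ARIA-H and other stable abnormalities.

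*Other routes to a signal exist.* Section 9.2 sends clinically relevant changes to the adverse event record, and the adverse event table is treatment-emergent. Under Section 3.2, changes judged not clinically significant go to the Data Review Committee. But ARIA is not an adverse event of special interest in Section 12.3.4, so a new asymptomatic ARIA-H need not reach the adverse event table. The MRI table is the only systematic count of such findings described in Section 11.5.

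**Conclusion.** The point holds as a mismatch between a stated counting rule and a stated purpose. In the double-blind phase the consequence is dilution and added noise, not loss of the comparison. Under the assumed rates of 6% and 2%, 70% to 90% of the absolute difference survives for b between 10% and 30%, while the ratio falls from 3.0 to between 1.31 and 1.09. These sizes rest on assumed incidence, assumed sample sizes, equal b in the arms and lesions that stay visible. The true loss may be nil if b is close to zero.

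The open-label conclusion does not depend on a particular value of b beyond its being above zero. Without a control arm, a presence count cannot separate old from new findings, and persisting lesions from the placebo period are credited to an active dose. The protocol should be changed because safety is its primary objective and the better count is cheap.

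**What to change.** Replace the Safety MRI sentence in Section 11.5 with a rule along these lines:

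- Tabulate by treatment group and by phase the number and percentage of subjects with new or increased ARIA-E, ARIA-H and other MRI abnormalities relative to a named reference scan.
- Use as denominator the subjects with that reference scan and at least one later scan in the phase.
- Show presence at the reference scan in a separate row, so that any imbalance between groups is visible.
- For the double-blind phase, use the pre-treatment parent-study scan where one exists. This protocol does not describe such a scan, so its availability must be confirmed.
- Where only the parent Month 6 scan exists, report against it and state that ARIA arising in the first six months of treatment is then classed as pre-existing.
- For the open-label phase, use the Week 52 scan. Section 9.1.3 places open-label randomization and dispensing after all Week 52 assessments, so this scan precedes open-label dosing.

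The cost is a few sentences and some extra comparison of existing reads at the core imaging laboratory. The rule asks for no new scan. Subjects without a reference scan drop out of the new-or-increased row, and their number should be stated.

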11.6. Interim Analysis

No prespecified interim analysis of unblinded data during the DB treatment phase is planned by the clinical team. However, depending on the recruitment, or in support of regulatory filings for upcoming studies, or for any other reason the Sponsor deems necessary, an unblinded review of safety and biomarker data prior to the last subject's completion of the DB treatment phase might be conducted by an internal Interim Analysis Committee. If any such review is conducted it will be documented in an Interim Analysis Committee charter prior to the unblinding. The

constitution of the Interim analysis committee will be documented in the Interim Analysis Committee charter and may include Sponsor study team members.

As noted in Section 5, when the parent study (e.g. 54861911ALZ2002 and potential future Phase 1b and 2 studies) is completed and its clinical database is closed, the randomization codes from the parent study will be released to the sponsor study team. Thus, the sponsor will be unblinded at that time, but the investigator and subjects will continue to be blinded to treatment during the DB treatment phase, until the last subject has completed that phase, and the database from that phase has been reviewed, corrected as necessary, and locked. At that point, the sponsor will perform analyses of key safety, biomarker, and efficacy variables, as detailed in a prespecified statistical analysis plan.

Following the sponsor's review of these analyses, information on an individual subject's treatment allocation during the DB phase will be made available upon request by the investigator. As subjects that remain in the study will all be receiving open label JNJ-54861911 at that time, and as no change or alteration of the locked database from the DB phase will be possible, there will be no bias introduced by this measure.

11.7. Data Review Committee

A DRC will be established to monitor the study data on an ongoing basis to ensure the continuing safety of the subjects enrolled in this study. The committee will meet periodically to review interim study data including the safety data as well as biomarker data (fluid [CSF, plasma] and imaging [vMRI]).

The CSF and Imaging biomarker data (e.g., CSF A β and CSF tau peptides or another marker of neurodegeneration; vMRI) will be reviewed periodically by the DRC to assess the continuous potential therapeutic effect of JNJ-54861911 over time on the pathophysiologic processes underlying AD in subjects asymptomatic at risk for developing Alzheimer's dementia.

After the review, the DRC will make recommendations regarding the safety and continuation of the study. The details will be provided in a separate DRC charter.

The DRC will consist of at least one medical expert in AD and at least one statistician. The DRC statistician will not be part of the Sponsor study team and as such will not otherwise be involved in the study conduct or the final statistical analysis of this study. The DRC responsibilities, authorities, and procedures will be documented in its charter.

12. ADVERSE EVENT REPORTING

Timely, accurate, and complete reporting and analysis of safety information from clinical studies are crucial for the protection of subjects, investigators, and the sponsor, and are mandated by regulatory agencies worldwide. The sponsor has established SOPs (SOPs) in conformity with regulatory requirements worldwide to ensure appropriate reporting of safety information; all clinical studies conducted by the sponsor or its affiliates will be conducted in accordance with those procedures.

12.1. Definitions

12.1.1. Adverse Event Definitions and Classifications

Adverse Event

An adverse event is any untoward medical occurrence in a clinical study subject administered a medicinal (investigational or non-investigational) product. An adverse event does not necessarily have a causal relationship with the treatment. An adverse event can therefore be any unfavorable and unintended sign (including an abnormal finding), symptom, or disease temporally associated with the use of a medicinal (investigational or non-investigational) product, whether or not related to that medicinal (investigational or non-investigational) product. (Definition per International Conference on Harmonisation [ICH])³⁴

This includes any occurrence that is new in onset or aggravated in severity or frequency from the baseline condition, or abnormal results of diagnostic procedures, including laboratory test abnormalities.

Note: The sponsor collects adverse events starting with the signing of the ICF (refer to Section 12.3.1, All Adverse Events, for time of last adverse event recording).

Serious Adverse Event

A serious adverse event based on ICH and EU Guidelines on Pharmacovigilance for Medicinal Products for Human Use is any untoward medical occurrence that at any dose:

- Results in death
- Is life-threatening
(The subject was at risk of death at the time of the event. It does not refer to an event that hypothetically might have caused death if it were more severe.)
- Requires inpatient hospitalization or prolongation of existing hospitalization
- Results in persistent or significant disability/incapacity
- Is a congenital anomaly/birth defect
- Is a suspected transmission of any infectious agent via a medicinal product
- Is Medically Important*

*Medical and scientific judgment should be exercised in deciding whether expedited reporting is also appropriate in other situations, such as important medical events that may not be immediately life threatening or result in death or hospitalization but may jeopardize the subject or may require intervention to prevent one of the other outcomes listed in the definition above. These should usually be considered serious.

If a serious and unexpected adverse event occurs for which there is evidence suggesting a causal relationship between the study drug and the event (e.g., death from anaphylaxis), the event must

be reported as a serious and unexpected suspected adverse reaction even if it is a component of the study endpoint (e.g., all-cause mortality).

Unlisted (Unexpected) Adverse Event/Reference Safety Information

An adverse event is considered unlisted if the nature or severity is not consistent with the applicable product reference safety information. For JNJ-54861911, the expectedness of an adverse event will be determined by whether or not it is listed in the Investigator's Brochure (Reference Safety Information included the IB).³⁷

Adverse Event Associated With the Use of the Drug

An adverse event is considered associated with the use of the drug if the attribution is possible, probable, or very likely by the definitions listed in Section 12.1.2.

